Appendix 3: Schedule of Events (IS Reduction plus COVID-19 Vaccine Dose)

Study Schedule	Days			Weeks						Months				
Time points	-5	0	3 ¹	1	2	3	4	5	6	3	6	9	12	For Cause ²
Visit #	01	02	03	04	05	06	07	08	09	10	11	12	13	FC
Visit Windows (+/-)	-	-	1d	1d	3d	3d	3d	3d	3d	2w	2w	2w	2w	-
General Assessments														
Study Contact ³	X	X		X	X	X	X	X	X	X	X		X	X
Medications (immunosuppression, PrEP, COVID-19 treatment)	X ⁴	→	→	→	→	→	→	→	→	X	X ⁵	X ⁵	X ⁵	X
Assessment of Events (AE, SAE, rejection, graft loss)	X	→	→	→	→	→	→	→	→	→	→	→	X	X
Clinical Laboratory Assessments														
Complete Blood Count with differential		X			X		X				X	X		X
Metabolic Panel ⁶		X								X	X			X
eGFR, serum creatinine (kidney)		X		X	X	X	X	X	X					
Hepatic Panel including direct bilirubin (liver)		X									X			
Quantitative Immunoglobulins		X									X			
SARS-CoV-2 PCR (nasal swab, clinical)		X ⁷					X			X	X	X	X	X
Investigational Intervention														
Immunosuppression Reduction	X	→	→	→	X ⁸									
COVID-19 mRNA Vaccine		X												
Central Laboratory Assessments														
SARS-CoV-2 PCR (nasal swab, research)		X					X			X	X		X	X
Oral fluid anti-N and anti-S immunoglobulin levels		X					X			X	X		X	X
Anti-SARS-CoV-2 S (Roche Elecsys [®])					X		X			X	X		X	X
Donor Specific Antibodies (kidney only)							X			X	X		X	
Antibody/Neutralization assays		X			X		X			X	X		X	X
Spike Protein (subset of sites)		X	X											
Proteomics		X	X ⁹				X							
Transcriptomics		X	X ⁸				X							
T and B Cell Assays		X			X		X			X	X		X	X

¹ May be a home draw. The spike protein will only be performed at a subset of clinical sites.² Unscheduled "for cause" visit for suspected rejection. Participants with confirmed COVID-19 will send in a nasal swab for research.³ Study contacts may be remote.⁴ Ensure the participant has not taken any medications since screening that would make them ineligible.⁵ Only PrEP and COVID-19 related treatment collected at these visits.⁶ Comprehensive metabolic panel at baseline, basic metabolic panel all other timepoints (see study definitions).⁷ If the Day 0 nasal swab is positive, IS reduction will be prematurely discontinued and participants will be followed until Day 30 for safety. This includes the Day 30 clinical labs, DSA and AE/SAE assessment. No further mechanistic blood will be collected.⁸ Participant will be informed to restart full IS the following day.⁹ These Day 3 assessments will only be collected on participants included in the Day 3 spike protein.

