3.3 Secondary Endpoints

3.3.1 Secondary Safety Endpoints

Local and systemic vaccine reactogenicity and/or allergy
Serious adverse events occurring during the 30 days following the additional dose of vaccine
Treated acute cell-mediated and/or antibody-mediated allograft rejection (clinical or biopsy-proven) within 60 days following the additional dose of vaccine
Development of de novo donor-specific anti-HLA antibody within 90 days of the vaccine
Graft loss within 60 days of the vaccine
Death within 60 days of the vaccine

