5.3 Risks Associated with IS Reduction

Any decrease in dose or frequency of immunosuppressive medications in a transplant recipient carries the risk of alloimmune activation leading to acute cellular rejection, subclinical rejection, acute or chronic antibody-mediated rejection, and/or the formation of de novo DSA. The inclusion criteria and the specific immunomodulatory strategies have been designed to minimize, but do not eliminate, this risk. Study participants undergoing IS reduction will be closely monitored for evidence of graft injury and will be returned to their baseline immunosuppressive regimen should graft injury be evident. In addition, subjects will be monitored for the development of de novo DSA throughout the study period.

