8.3.3 Follow-up Visits (All Participants)

Follow-up will occur at weeks 1, 2, 3, 4, 5, 6 and Months 3, 6, 9, and 12 following vaccine administration. Participants will have additional blood tests to monitor their graft function during the time they are on a reduced level of immunosuppression and for 1 month following resumption of their original regimen of immunosuppression. Identical blood testing schedules will take place for both the COVID-19 vaccine dose group and the IS reduction plus COVID-19 vaccine dose group. Kidney recipients will have their serum creatinine levels measured at the weekly visits. Liver recipients will have a hepatic panel (AST, ALT, alk phos, bilirubin, direct bilirubin) at the weekly visits.

The Week 4 visit is the primary endpoint visit. During these visits, participants will be asked about their general health, any new events, immunosuppression medications and their transplanted organ per the Schedule of Events in Appendix 2.

Blood and nasal swabs will be collected for assessments to be run in the clinical and research laboratories per the Schedule of Events in Appendix 2 or Appendix 3 based on group assignment. Nasal mid-turbinate swabs for SARS-CoV-2 PCR testing will be collected at baseline and Months 1, 3, 6, 9 and 12 following vaccine administration.

Participants will be instructed to contact the study team if they receive any COVID-19 testing at an outside lab during the course of the study. All instances of COVID-19 infection will be reported on the applicable electronic case report form.

A subset of participants will have a study visit on Day 3 to have blood drawn for a research laboratory study to detect the presence of SARS-CoV-2 spike protein generated in response to the vaccine.

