13.4.3 Analyses of Secondary and Other Endpoint(s)/Outcome(s)

All binary secondary endpoints will be analyzed using a Fisher exact test. Severe adverse events will be analyzed by calculating the incidence rate difference with a two-sided 95% confidence interval for immunoreduction vs no immunoreduction participants.

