13.5.2 Interim Analysis of Safety Data

Excess incidence of dnDSA in kidney transplant recipients: An interim analysis will be performed to look for evidence of an excess incidence of dnDSA in the IS reduction groups (those undergoing withdrawal of MMF; and those undergoing a decrease in CNI dose) as compared with those receiving an additional dose of vaccine alone. When fifteen subjects in each of these groups have reached day 30 in the study (study visit 4), the core HLA lab will determine whether de novo DSA is present. We will perform a similar analysis when fifty subjects in each group have reached day 30. At each of these two time points, the proportion with Class II dnDSA in each IS reduction group will be compared with the COVID-19 vaccine dose alone group using a one-sided Fisher exact test to determine if there is an excess incidence of Class II dnDSA, and the results presented to the DSMB for review

[figure not shown]

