Appendix 2: Schedule of Events (COVID-19 Vaccine Dose Alone)

Study Schedule	Days		Weeks						Months				
Time points	0	3 ¹	1	2	3	4	5	6	3	6	9	12	For Cause ²
Visit #	01	02	03	04	05	06	07	08	09	10	11	12	FC
Visit Windows (+/-)	-	1d	1d	3d	3d	3d	3d	3d	2w	2w	2w	2w	-
General Assessments													
Study Contact ³	X		X	X	X	X	X	X	X	X		X	X
Medications (immunosuppression, PrEP, COVID-19 treatment)	X ⁴	→	→	→	→	→	→	→	X	X ⁵	X ⁵	X ⁵	X
Assessment of Events (AE, SAE, rejection, graft loss)	X	→	→	→	→	→	→	→	→	→	→	X	X
Clinical Laboratory Assessments													
Complete Blood Count with differential	X			X		X			X	X		X	
Metabolic Panel ⁶	X								X	X		X	
eGFR, serum creatinine (kidney)	X		X	X	X	X	X	X					
Hepatic Panel including direct bilirubin (liver)	X									X			
Quantitative Immunoglobulins	X									X			
SARS-CoV-2 PCR (nasal swab, clinical)	X ⁷					X			X	X	X	X	X
Investigational Intervention													
COVID-19 mRNA Vaccine	X												
Central Laboratory Assessments													
SARS-CoV-2 PCR (nasal swab, research)	X					X			X	X		X	X
Oral fluid anti-N and anti-S immunoglobulin levels	X					X			X	X		X	X
Anti-SARS-CoV-2 S (Roche Elecsys®)				X		X			X	X		X	X
Donor Specific Antibodies (kidney only)						X			X	X		X	X
Antibody/Neutralization assays	X			X		X			X	X		X	X
Spike Protein (subset of sites)	X	X											
Proteomics	X	X ⁸				X							
Transcriptomics	X	X ⁷				X							
T and B Cell Assays	X			X		X			X	X		X	X

¹ May be a home draw. The spike protein will only be performed at a subset of clinical sites.

² Unscheduled "for cause" visit for suspected rejection. Participants with confirmed COVID-19 will send in a nasal swab for research.

³ Study contacts may be remote.

⁴ Ensure the participant has not taken any medications since screening that would make them ineligible.

⁵ Only PrEP and COVID-19 related treatment collected at these visits.

⁶ Comprehensive metabolic panel at baseline, basic metabolic panel all other timepoints (see study definitions).

⁷ If the Day 0 nasal swab is positive, the participant will be prematurely discontinued and followed until Day 30 for safety. This includes the Day 30 clinical labs, DSA and AE/SAE assessment. No further mechanistic blood will be collected.

⁸ These Day 3 assessments will only be collected on participants included in the Day 3 spike protein.

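### The For Cause visit for suspected rejection carries a central-lab DSA test in the control schedule but not in the IS reduction schedule; the cell should be checked and the two schedules aligned

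*Combined protocol and SAP*

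**What the plan says.** Appendices 2 and 3 each have a central-laboratory row whose label begins "Donor Specific Antibodies (kidney only". In Appendix 2 (vaccine alone) it is marked at Week 4, Months 3, 6 and 12, and For Cause. In Appendix 3 (IS reduction plus vaccine) it is marked at Week 4 and Months 3, 6 and 12, and the For Cause cell is empty. Footnote 2, the same in both appendices, defines that column: "Unscheduled 'for cause' visit for suspected rejection". No footnote explains the difference, and Section 8.4 on unscheduled visits names no DSA test.

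Other parts of the plan bear on this:

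- Section 5.3, on the risks of IS reduction, warns that "Any decrease in dose or frequency of immunosuppressive medications in a transplant recipient carries the risk of alloimmune activation" and says that "subjects will be monitored for the development of de novo DSA throughout the study period".
- Section 8.3.3, in its paragraph on graft-function monitoring, says: "Identical blood testing schedules will take place for both the COVID-19 vaccine dose group and the IS reduction plus COVID-19 vaccine dose group".
- Section 3.3.1 lists as a secondary safety endpoint "Development of de novo donor-specific anti-HLA antibody within 90 days of the vaccine", and Section 13.4.3 says "All binary secondary endpoints will be analyzed using a Fisher exact test".
- The Study Definitions Page defines DSA by central laboratory assessment.

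**The concern.** A kidney recipient seen for suspected rejection has a study DSA test if on control. On IS reduction, the same visit yields nasal, oral fluid, anti-spike, neutralization and cell samples, but no DSA. The missing test is in the arm that Section 5.3 identifies as carrying the alloimmune hazard.

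The second hypothesis in Section 2.1 holds that reduction brings no increase in rejection or de novo DSA. If one arm has an extra chance of detection at the moment of highest suspicion, part of any difference in the de novo DSA endpoint reflects the schedule and not the treatment. Here it would understate de novo DSA under reduction. A local DSA result would not fill the gap, because the study definition rests on the central laboratory.

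**Working it through.** **1. Is the cell really blank, or did PDF reading shift it?** I compared marks by column position in the two appendices.

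| Row | Appendix 2 marks | Appendix 3 marks | For Cause (App. 2 / App. 3) |
|---|---|---|---|
| DSA (kidney) | 5 | 4 | yes / no |
| Research PCR | 6 | 6 | yes / yes |
| Oral fluid | 6 | 6 | yes / yes |
| Roche anti-S | 6 | 6 | yes / yes |
| Neutralization | 7 | 7 | yes / yes |
| T and B cell assays | 7 | 7 | yes / yes |
| Complete blood count | 6 | 6 | no / yes (displaced) |
| Metabolic panel | 4 | 4 | no / yes (displaced) |

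Appendix 3 does contain displaced marks. The last three blood count marks sit at Month 6, Month 9 and For Cause, against Months 3, 6 and 12 in Appendix 2; the last metabolic panel mark sits under For Cause instead of Month 12. Those rows keep their number of marks. The DSA row loses one, and its four scheduled marks line up. That fits a blank cell better than a shift, but a mark lost in reading cannot be excluded.

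**2. How many visits are affected?** The plan gives no for-cause rate. Section 11.5 expects 5-6 rejections over the study; Sections 11.5 and 13.7 give 400 participants, 200 per arm. If for-cause visits were as frequent as rejections:

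- 5/400 × 200 = 2.5 per arm
- 6/400 × 200 = 3 per arm
- at three times that rate (the multiple used in the pausing rule): 7.5 to 9 per arm

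These counts cover both organs and the whole study. Kidney recipients within 90 days would be fewer; suspected rejections could exceed treated ones.

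**3. When could it alter the 90-day endpoint?** Taking Week 4 as Day 28 and Month 3 as Day 90, the ±2-week window in Section 8.7 puts the Month 3 draw at Days 76 to 104. The gap between scheduled draws is then 76 − 28 = 48 to 104 − 28 = 76 days. If visits spread evenly over the 29-day window (an assumption), 14/29 = 48% of Month 3 draws fall after Day 90, or 15/29 = 52% if Month 3 is Day 91. For those participants, Week 4 and any for-cause draw are the only results inside 90 days.

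**4. What could it do to the Fisher test?** The organ split is not given; assume 150 kidney recipients per arm. For k events against none, the two-sided p-value is 2 × C(150,k)/C(300,k):

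| Events | p |
|---|---|
| 2 v 0 | 0.50 |
| 4 v 0 | 0.12 |
| 5 v 0 | 0.060 |
| 6 v 0 | 0.030 |

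One missed event crosses 0.05 only near 6 v 0.

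**5. Does it reach the interim comparison?** Section 13.5.2 uses samples at day 30 ("When fifteen subjects in each of these groups have reached day 30 in the study", and again at fifty). The Week 4 draw is marked in both arms, so this comparison is essentially untouched.

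**6. After alignment.** Both arms have the same number of DSA occasions, 5 and 5 or 4 and 4. Sample size, power and alpha do not change.

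**The case against.** The strongest reply is that this is one cell in a visibly disordered table and probably a clerical slip. Scheduled DSA draws match, which suggests that unequal testing was not intended. That stands, and it is why the first step is to check the source.

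It can also be said that the text is not contradicted. The parity sentence in Section 8.3.3 concerns graft-function bloods and schedules, whereas For Cause visits are unscheduled; four scheduled draws arguably satisfy Section 5.3. This largely stands. The blank sits poorly with both sections, but the firm inconsistency is between the two appendices.

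Further, an empty cell does not forbid a test: central-laboratory blood is drawn at that visit in both arms, and Section 10 allows stored specimens to be used in future assays. This is true, but nothing commits the study to a DSA result from those samples.

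Stronger readings are tempting, and the documents do not support them:

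- *DSA is looked for less throughout the reduction arm.* Only for-cause visits differ.
- *A de novo DSA between Week 4 and Month 3 is found only in control.* That holds only for controls who have a for-cause visit in the interval and whose DSA does not persist; persistent DSA would usually appear at the next scheduled draw in either arm.
- *The DSMB loses its DSA information.* Its planned interim comparison uses day-30 samples.
- *One or two missed events would change the result.* By step 4 this needs about six events against none, and nothing in the plan suggests that.

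**Conclusion.** The discrepancy holds as the tables read, with moderate confidence that the blank is real. It makes ascertainment of a secondary safety endpoint depend on arm, and any bias favours a finding of no harm from reduction.

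Its size is small: perhaps 2.5 to 3 for-cause visits per arm over the study, on the assumption that they track expected rejections, and more if suspicion outruns treatment. What can be lost is mainly transient de novo DSA, the DSA status at the time of suspected rejection, and results for participants whose Month 3 draw falls after Day 90. The last route assumes that such a draw would not count towards the endpoint; the plan does not say. Liver recipients are outside the point, because DSA is kidney only in both schedules. The matter deserves correction because the remedy is simple, not because it threatens the trial's conclusions.

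**What to change.** 1. Check the For Cause DSA cell of Appendix 3 in the source document, together with the displaced blood count and metabolic panel marks.
2. If the cell is blank there, reconcile Appendices 2 and 3 so that the For Cause DSA entry is the same in both arms and consistent with Sections 5.3 and 8.3.3.
3. Optionally, add a de novo DSA sensitivity analysis restricted to scheduled draws. Even with identical entries, unequal numbers of for-cause visits could influence an open-label comparison; this analysis removes that route.

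The cost is one table cell and, if the test is kept in both arms, a few additional HLA assays at visits that already draw central-laboratory blood. The sensitivity analysis needs no new data.
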